## Statistical Analysis Plan

BAY 81-8973 (KOVALTRY) / 19855

Page: 14 of 15

### 6.4.3 Adverse Events of Special Interest (AESI)

The adverse events of special interest in this study are:

- *Development of factor VIII inhibitors.*

Inhibitor development as measured by Nijmegen-modified Bethesda assay will be summarized by time point and presented in participant listings. The purpose of the listing is to delineate the clinical factors which may be positively associated with development of the inhibitor. Confirmation of the first positive inhibitor titer ( $\geq 0.6$  BU/mL) which is developed during the treatment with study drug will require repeat measurement of a second different sample. If the repeated inhibitor result is  $< 0.6$  BU/mL without intervention, the inhibitor is not confirmed and should not be reported as an SAE.

Inhibitors will be classified as being either low titer ( $\geq 0.6$  BU/mL and  $\leq 5$  BU/mL) or high titer based upon persistence of an inhibitor  $> 5$  BU/mL. Proportions of participants with inhibitor will be presented in an overview table. Exact Clopper Pearson CI for the proportion will be given if any inhibitor exists.

- *Hypersensitivity and allergic reactions including skin related and systemic reactions, such as anaphylactic reactions, (seriousness should be a case by case decision)*

The incidence of AEs, and AESI will be summarized and described for each age group and also for the overall study population combined.

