### 2.3.1 Risk Assessment

Potential Risk of Clinical Significance	Summary of Data/ Rationale for Risk	Mitigation Strategy
Important identified risks: 
 
Development of factor VIII inhibitors
 
Hypersensitivity and allergic reactions
 
	
Development of factor VIII inhibitors: The formation of neutralizing antibodies (inhibitors) to FVIII is a known complication in the management of individuals with hemophilia A and a class effect for all FVIII products. For previously untreated patients (PUPs), the risk to develop inhibitors is considered very common (approximately 30% to 50%), whereas the risk for PTPs is considered uncommon (<1%).
 
Hypersensitivity and allergic reactions: Hypersensitivity reactions, including anaphylaxis, are possible with KOVALTRY. No anaphylactic reactions have been reported with KOVALTRY. Allergic type hypersensitivity reactions are possible with KOVALTRY. The product may contain traces of hamster or mouse proteins, which in some patients may cause allergic reactions.
	
The informed consent will outline the important identified and potential risks.
 
Inhibitor titer is assessed at scheduled study visits.
 
Planned time points for all safety assessments are provided in the Schedule of Activities [Section 1.3].

Study Intervention - KOVALTRY		
Drug infusion: This procedure can cause pain or bruising at the site of the infusion.	The study treatment is administered as intravenous infusion [see Section 6.1].	Study participants will be informed of these potential risks in the informed consent.
Study Procedures		
Blood draw: This procedure can cause discomfort from the needle, pain, and bruising at the site of the draw.  There is rarely any infection. Drug infusion: This procedure can cause pain or bruising at the site of the infusion.	Blood samples will be obtained at baseline to confirm study eligibility. As outlined in Section 7.1 and Section 7.2, there will be additional blood draws at scheduled study visits for FVIII recovery, FVIII inhibitor assessment, and for a subset of participants in Part A, additional PK analysis sampling.	Study participants will be informed of these potential risks in the informed consent.

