#### 9.2.2 Sample Size Determination in Part B (PUPs/MTPs)

To fulfill the post-approval commitment enforced for KOVALTRY, the Sponsor is committed to collecting additional efficacy and safety data in previously untreated Chinese severe hemophilia A patients, in line with the CDE Technical Guideline on the Clinical Investigation of Recombinant Human Coagulation Factor VIII.

It is considered feasible to enroll approximately 6 PUPs/MTPs in Part B of this study.

Part B of this study is designed in accordance with the multinational clinical trial of KOVALTRY in previously untreated/minimally treated patients, LEOPOLD Kids Part B, where the annualized number of bleeds that occur within 48 hours after a prophylaxis infusion was the primary efficacy endpoint.

A mean of 1.9 (standard deviation 3.3) was observed for this ABR in LEOPOLD Kids Part B. Assuming the same distribution, the point estimate for the ABR within 48 hours after a prophylaxis infusion of 6 patients will be smaller than 2.9 with a probability of more than 80% (based on simulations of data for 6 patients from a negative binomial distribution).

In addition, in the SIPPET study (a multinational, prospective, randomized trial that assessed the incidence of FVIII inhibitors among PUPs treated with plasma-derived FVIII

containing von Willebrand factor or rFVIII products), the incidence of inhibitor development for the class of rFVIII products was 44.5% (95% CI: 34.7% to 54.3%).

Therefore, the true inhibitor rate for PUPs/MTPs is assumed to be within the range of 35% to 54%. With a sample size of 6 PUPs/MTPs, there is at least 92% power to observe at least 1 participant developing an inhibitor if the rate is between 35% and 54%. In case an event of inhibitor development is not observed, this sample size would provide more than 90% reassurance that the inhibitor rate should be no more than 35%.

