#### 9.4.4 Safety Analyse(s)

Safety analysis will be performed separately for Part A, Part B, and Optional ITI Treatment.

Safety data will be summarized for all participants in the safety population for overall and by age groups respectively for Part A and summarized for Part B. Laboratory findings, AEs, concomitant medications, vital signs, and medical history data will be provided in participant listings. Laboratory values and vital signs will be summarized.

Individual listings of AEs (including age, AEs as reported, start, duration, severity, relation to study drug) will be provided. An AE is defined as treatment-emergent if it started or deteriorated after the first infusion and not later than three days after the last infusion in Part A or Part B. The incidence of treatment-emergent AEs will be summarized using the Medical Dictionary for Regulatory Affairs (MedDRA).

Inhibitor development as measured by Nijmegen-modified Bethesda assay will be summarized by time point and presented in participant listings. The purpose of the listing is to delineate the clinical factors that may be positively associated with development of the inhibitor. Confirmation of the first positive inhibitor titer (Bethesda  $\geq 0.6$  BU/mL) will require repeat measurement of a second different sample.

If the repeated inhibitor result is  $<0.6$  BU/mL without intervention, the inhibitor is not confirmed and should not be reported as an SAE. Inhibitors will be classified as being either low titer ( $\geq 0.6$  BU/mL and  $\leq 5$  BU/mL) or high titer based upon persistence of an inhibitor  $>5$  BU/mL. Proportions of participants with inhibitor will be presented in an overview table. Exact Clopper Pearson CI for the proportion will be given if any inhibitor exists.

The rate of inhibitor development will be summarized and described for both the pediatric and the adolescent/adult populations, and for the overall study population combined.

Safety analysis for optional ITI treatment is based on the ITI treatment set. Laboratory findings (inhibitor titer and recovery), AEs, concomitant medications, and EDs will be provided in participant listings. More details will be provided in the SAP.

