### 1. Introduction

This statistical analysis plan (SAP) version 2.0 is based on the finalized Protocol Version 2.0, dated 22 OCT 2020.

The protocol version 2.0, dated 22 OCT 2020 is integration of the original protocol version 1.0, dated 29 Jan 2020 and the amendment 1.

This SAP describes the study objective, study design, analysis sets, all endpoints, and statistical analysis methods. Complete details of Tables, Listing and Figures (TLFs) specifications as well as dataset details and data handling specifications will be provided in separate “TLF specifications” and “Analysis Datasets” documents as an integral part of this SAP.

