### Part A (PTPs)

Part A will assess the efficacy, safety, and PK of KOVALTRY in previously treated Chinese children and adolescents/adults with severe hemophilia A. Part A is planned to investigate a total of 42 PTPs (30 children and 12 adolescents/adults). PK will be assessed in a subset of 12 children (<12 years) and in 12 adolescents/adults ( $\geq 12$  years).

Efficacy and safety data for use of KOVALTRY for treatment of bleeding episodes will also be collected.

- Study participants will be treated for 6 months with the following dose regimen for prophylaxis according to the prescribing information for KOVALTRY:
  - Study participants  $\leq 12$  years of age: 25 to 50 IU of KOVALTRY per kg body weight twice weekly, three times weekly, or every other day according to individual requirements for 6 months.
  - Study participants  $> 12$  years: 20 to 40 IU of KOVALTRY per kg of body weight two or three times per week according to individual requirements for 6 months.
- Part A will include 5 study visits (Screening, Baseline, Visit 3/Month 1, Visit 4/ Month 2, Visit 5/Final study visit/Early Termination). All participants will also receive a safety follow-up call approximately 2 weeks after the final study visit.

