### 4. General Statistical Considerations

#### 4.1 General Principles

There is no confirmatory comparison planned for this study, study results will be numerically evaluated.

Part A and Part B will be analyzed separately, both for efficacy and safety. The optional ITI treatment period will only be considered for the safety analysis.

The efficacy and safety analysis will be presented as summary statistics by age groups (<12 or  $\geq 12$  years of age) in Part A.

The statistical evaluation will be performed by using the software package SAS release 9.2 or higher (SAS Institute Inc., Cary, NC, USA). All variables will be analyzed by descriptive statistical methods. The number of data available and missing data, mean, standard deviation, minimum, quartiles, median, and maximum will be calculated for metric data. Frequency tables will be generated for categorical data.

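### The exact confidence interval for the inhibitor proportion is planned only when an inhibitor is seen, so a zero count, the likeliest Part A result, gets no upper bound

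*SAP*

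**What the plan says.** SAP 6.4.3 plans the inhibitor results as a summary by time point, participant listings and a table: "Proportions of participants with inhibitor will be presented in an overview table". The only measure of precision is conditional: "Exact Clopper Pearson CI for the proportion will be given if any inhibitor exists". Protocol 9.4.4 contains the same sentence. Neither gives a confidence level or says whether the interval is one- or two-sided, and neither plans another bound when no inhibitor is found.

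On the groups to be reported, SAP 4.1 says "Part A and Part B will be analyzed separately, both for efficacy and safety". Protocol 9.4.4 adds "The rate of inhibitor development will be summarized and described for both the pediatric and the adolescent/adult populations" and goes on to include the combined population.

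Two other places bear on how likely a zero count is. Protocol 2.3.1 contrasts the high risk in previously untreated patients with that in previously treated patients: "whereas the risk for PTPs is considered uncommon", with a figure below 1%. For Part B, protocol 9.2.2 (repeated in SAP 3.1.2) assumes a rate of 35% to 54% and considers the zero case directly: "In case an event of inhibitor development is not observed, this sample size would provide more than 90% reassurance" that the rate is at most 35%.

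**The concern.** Inhibitor development is a named safety endpoint and an adverse event of special interest in both parts. With no hypothesis test planned, the study's contribution on this endpoint is an estimate and its precision. The rule makes the reporting of precision depend on the observed result and drops it where it is most needed. A table showing 0% with no limit is easily read as confirming the rate below 1% cited for previously treated patients, which samples of 42, 30 and 12 cannot do.

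There are two further gaps in the sentence. It does not say whether the condition is applied per part, per age group or across the whole study, so two programmers could produce different tables from the same data. In Part B, it withholds the interval in the one case where the protocol's 35% statement would be used.

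**Working it through.** **Inputs.** Part A: 42 participants, 30 children and 12 adolescents/adults (SAP section 3). Part B: about 6 (protocol 9.2.2, SAP 3.1.2). Inhibitor rate: below 1% in Part A (protocol 2.3.1), 35% to 54% in Part B, with a cited class rate of 44.5% (protocol 9.2.2). All planned participants are taken as evaluable. The 95% level is an assumption.

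**The plan's own figures.** The chance of at least one inhibitor among 6 is 1 − (1 − p)^6:

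- p = 0.35: 1 − 0.65^6 = 1 − 0.0754 = 92.5%
- p = 0.54: 1 − 0.46^6 = 1 − 0.0095 = 99.1%

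Both agree with the stated minimum of 92%. The same 92.5% reproduces the reassurance of more than 90% after 0/6, read as a one-sided statement. These planning figures are correct.

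**How often the rule suppresses the interval.** P(zero) = (1 − p)^n.

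| Group | Rate | P(zero) |
|---|---|---|
| Part A, n = 42 | 1% | 0.99^42 = 65.6% |
| Part A, n = 42 | 0.5% | 0.995^42 = 81.0% |
| Part A, n = 42 | 0.1% | 0.999^42 = 95.9% |
| Children, n = 30 | 1% | 0.99^30 = 74.0% |
| Adolescents/adults, n = 12 | 1% | 0.99^12 = 88.6% |
| Part B, n = 6 | 35% | 0.65^6 = 7.5% |
| Part B, n = 6 | 44.5% | 0.555^6 = 2.9% |
| Part B, n = 6 | 54% | 0.46^6 = 0.9% |

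The Part A values at 1% are minimum chances, because the protocol puts the rate below 1%.

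**What is lost.** At zero events the lower limit is 0 and the upper limit is 1 − 0.025^(1/n) (two-sided 95%) or 1 − 0.05^(1/n) (one-sided 95%).

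| Result | Two-sided 95% upper | One-sided 95% upper |
|---|---|---|
| 0/42 | 8.4% | 6.9% |
| 0/30 | 11.6% | 9.5% |
| 0/12 | 26.5% | 22.1% |
| 0/6 | 45.9% | 39.3% |

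For comparison, the two-sided 95% intervals that the plan would print after one event are 0.06% to 12.6% for 1/42 and 0.4% to 64.1% for 1/6.

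**Level and sidedness.** For 0/6 the 95% upper limit excludes the cited 44.5% class rate if one-sided (39.3%) and includes it if two-sided (45.9%). The choice changes what the table appears to show.

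**Scope of the condition.** Scope matters within Part A when exactly one age group has an event. At a 1% rate the chance is 0.740 × (1 − 0.886) + 0.886 × (1 − 0.740) = 31.5%. This is the top of the range: the same formula gives about 18% at 0.5% and about 4% at 0.1%.

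**The case against.** The strongest objection concerns scope. If the condition applies to the whole study, any Part B inhibitor triggers the intervals everywhere. With a Part B rate of 35% and a Part A rate of 1%, the chance of at least one inhibitor in the study is 1 − 0.0754 × 0.656 = 95%, so 0/42 would nearly always get its interval. The arithmetic is right, but the reading is strained: both documents analyse safety separately by part, and nothing suggests that a Part B event should decide what is printed for Part A.

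The second objection is that little is lost. The study is descriptive, 0/n still appears in the table, and a reader can compute the upper limit from n. This stands as a limit on severity. It is not a reason to keep the condition, since readers should not have to supply the precision of a principal safety endpoint themselves.

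Third, level and sidedness may be settled elsewhere. SAP section 1 says "Complete details of Tables, Listing and Figures (TLFs) specifications as well as dataset details and data handling specifications will be provided in separate" documents, which are not available here, and the Part A sample-size calculation uses 95%. That is a fair answer on those details. It does not answer the main point, because the condition is a rule stated in both documents and table shells that follow the SAP would implement it.

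Finally, a zero count in Part B is unlikely under the assumed rates, and the sample-size text already gives a conclusion for it. Both are true, but that text is a planning statement and commits the analysis to no output.

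**Conclusion.** The concern holds. As written, and on the natural reading by part or by group, the plan reports no interval for the most probable Part A outcome: a probability of at least 65.6% for 0/42 when the rate is 1% or lower. The suppressed two-sided 95% upper limits are 8.4%, 11.6% and 26.5% for Part A overall, children and adolescents/adults, all far above the cited rate of below 1%. For Part B the missing limit after 0/6 would be 45.9%, in a case with a probability of 0.9% to 7.5% under the assumed rates. Nothing in the method requires the condition.

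The conclusion rests on full planned enrolment being evaluable for inhibitors and on a 95% level. This should be corrected, but it is a reporting defect: no data, estimate or decision rule is affected.

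**What to change.** In SAP 6.4.3 and protocol 9.4.4, replace the conditional sentence with:

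> Two-sided 95% exact Clopper-Pearson CIs for the proportion of participants with inhibitor will be given for Part A overall, for each Part A age group and for Part B, whatever the number observed, including zero.

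This settles level, sidedness and scope together. It takes the combined population in protocol 9.4.4 to be Part A overall, in line with the separate analysis of the parts. If a figure pooled across both parts is also intended, add it to the list.

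Optionally, in protocol 9.2.2 and SAP 3.1.2, label the reassurance statement as one-sided at 92.5% and note the 95% upper limits for 0/6 (39.3% one-sided, 45.9% two-sided). The statement is correct as it stands, so this only helps the reader compare it with the reported interval.

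The cost is one sentence in each document and a few table cells, with no new data and no effect on sample size. The SAP change alone would secure the output, and the protocol sentence can be aligned at its next amendment.

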### 6.4.4 Vital signs

Vital signs at each visit and change from baseline will be summarized.

## 7. Document history and changes in the planned statistical analysis

Version	Date	Action
Version 1.0	18 September 2020	
Version 2.0	17 November 2021	

• Updated according to Global Integrated Clinical Study Protocol version 2.0.

• Updated the Compliance calculation in section 6.1.1

• Detail the ABR of all bleeding episodes in section 6.2.1

## Statistical Analysis Plan

---

BAY 81-8973 (KOVALTRY) / 19855

Page: 15 of 15

